## 9.5 Study Assessments

## 9.5.1 Assessments

Details for all assessment in the Extension Phase can be found in Appendix 3.

### 9.5.1.1 Demography

Subject demography information will be collected at the Screening Visit. Demography information includes date of birth (or age), sex, and race/ethnicity.

### 9.5.1.2 Baseline Assessments

### MEDICAL HISTORY AND PHYSICAL EXAMINATIONS

Medical history, including and surgical history and current medical conditions, will be recorded. All medical and surgical history within 2 years must be noted in the Medical History and Current Medical Conditions CRF.

Physical examinations (comprehensive or symptom-directed) will be performed as designated in the Schedule of Procedures/Assessments (Table 4 and Table 5). A comprehensive physical examination will include evaluations of the head, eyes, ears, nose, throat, neck, chest (including

heart and lungs), abdomen, limbs, skin, and a complete neurological examination. Documentation of the physical examination will be included in the source documentation at the site. Significant findings at the Screening Visit will be recorded on the Medical History and Current Medical Conditions CRF. Changes from screening physical examination findings that meet the definition of an AE will be recorded on the Adverse Events CRF.

#### EPILEPSY MEDICAL HISTORY

In addition to standard medical history, epilepsy medical history will be documented for each subject.

#### 9.5.1.3 Efficacy Assessments

#### SEIZURE COUNTS

Efficacy will be assessed by seizure counts and types as recorded on a study specific seizure diary. Diaries will be dispensed to all subjects at each visit as described in Table 4 and Table 5. The diary is to be completed daily, by the parent/guardian. All seizures will be recorded. At each visit the parent/guardian will be instructed by the site personnel as to how to complete the diary and reminded that they must return the diary at their next scheduled clinic visit and at the Early Discontinuation and Follow-up Visits (if applicable). To ensure correct seizure classification, the physician investigator should review the diary with the parent/guardian at all visits. Parents/guardians must be counseled if diary compliance is not satisfactory (ie, missed three or more consecutive daily diary entries).

#### CLINICAL GLOBAL IMPRESSION OF CHANGE

The CGI will be used to evaluate perceived seizure frequency and severity, the occurrence of AEs, and overall functional status of the subject. The evaluations of CGIS and CGIC both use a 7-point scale. For the CGI-S, 1 = normal, not at all ill and 7 = extremely ill, and for the CGI-C, 1 = very much improved and 7 = very much worse.

9.5.1.4 Pharmacokinetic, Pharmacodynamic, Pharmacogenomic, and Other Biomarker Assessments

#### PHARMACOKINETIC ASSESSMENTS

Blood samples (1.0 mL) for plasma will be collected from all subjects at pre-specified visits for the determination of perampanel concentrations, as detailed in Table 4.

For subjects aged 1 to less than 24 months: Dosing should occur once daily before bedtime in the evening (revised per Amendment 02). On the day of the PK sampling, subjects will have to attend the clinic any time during the day to provide blood sampling for PK analysis and to enable close monitoring of the subjects for safety and tolerability. One blood sample (1.0 mL) for the determination of perampanel plasma concentrations will be collected during the specified visits. The resulting plasma sample will be aliquoted into 2 Microtainer tubes. Plasma samples will be analyzed using a validated small-volume plasma assay method.The

date and time of perampanel dosing for 3 days before a PK visit and time of blood PK sampling will be recorded.

For subjects aged 2 to less than 4 years, dosing should occur once daily before bedtime in the evening, including the evening before the PK visit during Titration Period (Visit 5 for non-EIAED subjects, or Visit 6 for EIAED subjects). The dosing date and time of the last 3 doses before Titiration Period PK visit will be recorded. Note: For PK visits during Maintenance Period (ie, Visits 7 and 8 for non-EIAED subjects, or Visits 8 and 9 for EIAED subjects), as 2 PK samples (1 predose and 1 early postdose [within 1 to 5 hours after dosing]) are to be collected, the following steps are to be followed (revised per Amendment 02):

- Study drug administration in the evening immediately before the PK visits during Maintenance Period will be withheld. All other AEDs should be administered per the subject's usual AED regimen.
- During each of the Maintenance Period PK visits, collect predose PK sample. Then administer study drug on site, followed by early postdose PK sample collection (within 1 to 5 hours after dose administration).
- Bedtime dosing will resume beginning in the evening of the Maintenance Period PK visits.
- The dosing date and time of the study drug dose administered on-site during each Maintenance Period PK visit, as well as the last 2 doses before will be recorded. (revised per Amendment 02)

A population PK approach will be used to characterize the PK of perampanel.

An approximation of the total blood volume that will be drawn from each subject during the study is presented in Appendix 2.

For all PK samples, including the unscheduled PK samples collected, if any, before dose up-titrations beyond 6 mg/day (non-EIAED subjects) or 8 mg/day (EIAED subjects), plasma concentrations of perampanel will be quantified by a validated liquid chromatography-tandem mass spectrometry (LC-MS/MS) analytical method in sodium heparinized human plasma samples. (revised per Amendment 02)

Blood also will be drawn where possible at the first report of a serious adverse event (SAE) or severe unexpected AE and at its resolution.

A detailed description of collection, handling, and shipping procedures of PK samples will be provided in the Laboratory Manual to be provided to the sites.

#### Pharmacodynamic, Pharmacogenomic, and Other Biomarker Assessments

Not applicable.

#### 9.5.1.5 Safety Assessments

Safety will be assessed by monitoring and recording of all AEs and SAEs, clinical labs (ie, hematology and blood chemistry), vital signs, ECGs, medical history, and physical and neurological examinations.

Growth will be assessed for this age population by measurement of height, weight, head circumference, thyroid function and insulin-like growth factor-1 (IGF-1) testing.

Details of the timing of all safety assessments are presented in Table 4.

#### Adverse Events and Events Associated With Special Situations

An AE is any untoward medical occurrence in a patient or clinical investigation subject administered an investigational product. An AE does not necessarily have a causal relationship with the medicinal product. For this study, the study drug is perampanel (E2007).

The criteria for identifying AEs in this study are:

- Any unfavorable and unintended sign (including an abnormal laboratory finding), symptom, or disease temporally associated with the use of an investigational product, whether or not considered related to the investigational product (Note: Every sign or symptom should not be listed as a separate AE if the applicable disease [diagnosis] is being reported as an AE)
- Any new disease or exacerbation of an existing disease
- Any deterioration in nonprotocol-required measurements of a laboratory value or other clinical test (eg, ECG or x-ray) that results in symptoms, a change in treatment, or discontinuation of study drug
- Recurrence of an intermittent medical condition (eg, headache) not present pretreatment (Baseline)
- An abnormal laboratory test result should be considered an AE if the identified laboratory abnormality leads to any type of intervention, withdrawal of study drug, or withholding of study drug, whether prescribed in the protocol or not

All AEs observed during the study will be reported on the CRF. All AEs, regardless of relationship to study drug or procedure, should be collected beginning from the time the subject signs the study ICF through the last visit and for 28 days following study drug discontinuation. Subjects who fail screening primarily due to AE(s) must have the AE(s) leading to screen failure reported on the Screening Disposition CRF. SAEs will be collected for 28 days after the last dose.

Abnormal laboratory values should not be listed as separate AEs if they are considered to be part of the clinical syndrome that is being reported as an AE. It is the responsibility of the investigator to review all laboratory findings in all subjects and determine if they constitute an AE. Medical and scientific judgment should be exercised in deciding whether an isolated laboratory abnormality should be classified as an AE. Any laboratory abnormality considered to constitute an AE should be reported on the Adverse Event CRF.

Abnormal ECG QTc results, if not otherwise considered part of a clinical symptom that is being reported as an AE, should be considered an AE if the QTc interval is more than 450 msec and there is an increase of more than 60 msec from baseline. Any ECG abnormality that the investigator considers as an AE should be reported as such.

All AEs must be followed for 28 days after the subject's last dose, or until resolution, whichever comes first. All SAEs must be followed to resolution or, if resolution is unlikely, to stabilization.

## Every effort must be made by the investigator to categorize each AE according to its severity and its relationship to the study treatment.

#### ASSESSING SEVERITY OF ADVERSE EVENTS

AEs will be graded on a 3-point scale (mild, moderate, severe) and reported in the detail indicated on the CRF. The definitions are as follows:

Mild Discomfort noticed, but no disruption of normal daily activity

Moderate Discomfort sufficient to reduce or affect normal daily activity

Severe Incapacitating, with inability to work or to perform normal daily activity

The criteria for assessing severity are different than those used for seriousness (see Section 9.5.1.5 for the definition of an SAE).

#### ASSESSING RELATIONSHIP TO STUDY TREATMENT

Items to be considered when assessing the relationship of an AE to the study treatment are:

- Temporal relationship of the onset of the event to the initiation of the study treatment
- The course of the event, especially the effect of discontinuation of study treatment or reintroduction of study treatment, as applicable
- Whether the event is known to be associated with the study treatment or with other similar treatments
- The presence of risk factors in the study subject known to increase the occurrence of the event
- The presence of nonstudy, treatment-related factors that are known to be associated with the occurrence of the event

#### CLASSIFICATION OF CAUSALITY

The relationship of each AE to the study drug will be recorded on the CRF in response to the following question:

Is there a reasonable possibility that the study drug caused the AE?

- Yes (related) A causal relationship between the study drug and the AE is a reasonable possibility.
- No (not related) A causal relationship between the study drug and the AE is not a reasonable possibility.

#### Serious Adverse Events and Events Associated With Special Situations

A serious adverse event (SAE) is any untoward medical occurrence that at any dose:

- Results in death
- Is life-threatening (ie, the subject was at immediate risk of death from the AE as it occurred; this does not include an event that, had it occurred in a more severe form or was allowed to continue, might have caused death)
- Requires inpatient hospitalization or prolongation of existing hospitalization
- Results in persistent or significant disability/incapacity
- Is a congenital anomaly/birth defect (in the child of a subject who was exposed to the study drug)

Other important medical events that may not be immediately life-threatening or result in death or hospitalization but, when based on appropriate medical judgment, may jeopardize the subject or may require intervention to prevent one of the outcomes in the definition of SAE listed above should also be considered SAEs. Medical and scientific judgment should be exercised in deciding whether expedited reporting is appropriate in such situations.

In addition to the above, events associated with special situations include AEs associated with study drug overdose, misuse, abuse, or medication error. These events associated with special situations are to be captured using the SAE procedures but are to be considered as SAEs only if they meet one of the above criteria. All AEs associated with special situations are to be reported on the CRF whether or not they meet the criteria for SAEs.

All SAEs must be followed to resolution or, if resolution is unlikely to stabilization.

The following hospitalizations are not considered to be SAEs because there is no "adverse event" (ie, there is no untoward medical occurrence) associated with the hospitalization:

- Hospitalizations for respite care
- Planned hospitalizations required by the protocol
- Hospitalization planned before informed consent (where the condition requiring the hospitalization has not changed after study drug administration)

- Hospitalization for administration of study drug or insertion of access for administration of study drug
- Hospitalization for routine maintenance of a device (eg, battery replacement) that was in place before study entry

If possible, a blood sample for the measurement of study drug plasma concentration should be drawn at the first report of an SAE or a severe unexpected AE and at its resolution.

#### LABORATORY MEASUREMENTS

Blood collections for clinical laboratory testing, including hematology, and chemistry, are summarized in Table 3. Subjects should be in a supine position during blood collection. In addition, blood samples for the determination of thyroid function (thyroid stimulating hormone [TSH], free triiodothyronine [fT3], free thyroxine [fT4]), and IGF-1 levels will be collected The Schedule of Procedures/Assessments (Table 4) shows the visits and timepoints at which blood for all clinical laboratory tests will be collected in the study (Core Study). An approximation of total blood volume that will be drawn for each subject during the study is presented in Appendix 2. (revised per Amendment 02)

Category	Parameters
Hematology	Hematocrit, hemoglobin, platelets, RBC count, and WBC count with differential (basophils, eosinophils, lymphocytes, monocytes, neutrophils)
Chemistry	
Electrolytes	Chloride, potassium, sodium
Liver function tests	Alanine aminotransferase, alkaline phosphatase, aspartate aminotransferase, gamma glutamyl transpeptidase, direct bilirubin, total bilirubin
Renal function tests	Blood urea/blood urea nitrogen, creatinine
Other	Albumin, calcium, cholesterol, globulin, glucose a , lactate dehydrogenase, phosphorus, total protein, triglycerides a , uric acid, thyroid (TSH, fT3, fT4) and IGF-1 tests
	•

Table 3	Clinical	Laboratory	Tests
---------	-----------------	------------	-------

fT3 = free triiodothyronine, fT4 = free thyroxine, IGF = insulin-like growth factor, RBC = red blood cell, TSH = thyroid stimulating hormone, WBC = white blood cell.

a. Samples for glucose and triglycerides will be taken under fasted conditions, whenever practically feasible. (revised per Amendment 02)

Clinical laboratory tests during the study will be performed by a central laboratory. All clinical laboratory tests are to be performed at the central laboratory. At Screening/Baseline (Visit 1), use of local laboratory test results (hematology, clinical chemistry, thyroid function and IGF-1 test), if obtained within 4 weeks before Visit 1, may be allowed in lieu of blood draw for central laboratory analyses, provided that the subject's local laboratory tests were performed at a Clinical Laboratory Improvement Amendments (CLIA)-certified laboratory. In these cases,

to enable safety evaluation (eg, to assess whether there are treatment-emergent shifts in laboratory values from baseline), all post-baseline labs must be conducted at the same local laboratory using same assays as those used at Screening/Baseline. In other cases where unscheduled laboratory samples need to be taken and immediately analyzed to address a safety concern, blood samples will be split (or 2 samples drawn) to allow for a local laboratory analysis in addition to the central laboratory. Laboratory certification, as well as normal assay range for each of local laboratory tests run, will be collected as available and will be included in the clinical study report for this protocol. (revised per Amendment 02)

For laboratory abnormalities meeting the criteria of SAEs (see Section 9.5.1.5), the site must fax or email the SAE report including the laboratory report (as regionally required) to the sponsor using the SAE form (see Section 9.5.4.1).

#### VITAL SIGNS WEIGHT, HEIGHT, AND HEAD CIRCUMFERENCE MEASUREMENTS

Vital sign measurements (ie, systolic and diastolic blood pressure [BP] [mmHg], pulse [beats per minute], respiratory rate [per minute], body temperature [in centigrade]), and growth parameters including measurement of height, weight (kg), head circumference, will be obtained at the visits designated in the Schedule of Procedures/Assessments (Table 4). Blood pressure and pulse will be measured after the subject has been sitting or supine, for 5 minutes. All BP measurements should be performed on the same arm, preferably by the same person.

#### PHYSICAL EXAMINATIONS

Physical examinations will be performed as designated in the Schedule of Procedures/Assessments (Table 4). Documentation of the physical examination will be included in the source documentation at the site. Only changes from screening physical examination findings that meet the definition of an AE will be recorded on the Adverse Events CRF.

#### ELECTROCARDIOGRAMS

Electrocardiograms will be obtained as designated in the Schedule of Procedures/Assessments (Table 4).

ECGs should preferably be recorded prior to blood draws when both are scheduled at the same visit. However, if for any reason blood draws occur before ECG recording, then the ECG must be recorded at a minimum of 30 minutes after the blood draw. The subject should be relaxed and must be in a supine position at least 5 minutes prior to recording an ECG. The ECG will be reviewed by the investigator (paper or electronic tracing) and will be available for comparison with subsequent ECGs by the investigator.

If the subject has a normal ECG baseline reading, but during any visit thereafter there is any clinically significant ECG abnormality (as determined by the investigator), 3 consecutive ECGs separated by 5 to 10 minutes will be performed to confirm the abnormality at that visit.

ECGs will be transmitted the same day they are taken to the central ECG laboratory for evaluation. The ECG will be interpreted by a Central ECG laboratory cardiologist. The results of this over-read will be transmitted to the investigator. The cardiologist at the central ECG laboratory will be available to consult with the investigator(s) on the interpretation of individual subject ECG recordings, as needed. The corrected interval, as reported to the investigator by the Central ECG laboratory, will be QTc Fridericia (QTcF).

An ECG abnormality may meet the criteria of an AE as described in this protocol (see Section 9.5.1.5) and the CRF Completion Guidelines. In these instances, the AE corresponding to the ECG abnormality will be recorded on the Adverse Events CRF.

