#### Pharmacokinetic Assessments (Core Study only)

Blood samples (1.0 mL) for plasma will be collected from all subjects at prespecified visits for the determination of perampanel plasma concentrations. On the day of PK sampling, subjects will attend the clinic any time during the day to provide blood sampling for PK analysis and to enable close monitoring of the subjects for safety and tolerability. The resulting plasma sample will be aliquoted into 2 Microtainer® tubes.

For subjects aged 1 to less than 24 months, dosing should occur once daily before bedtime in the evening. The dosing date and time of the last 3 doses before each PK visit will be recorded. (revised per Amendment 02)

For subjects aged 2 to less than 4 years, dosing should occur once daily before bedtime in the evening, including

the evening before the PK visit during Titration Period (Visit 5 for non-EIAED subjects, or Visit 6 for EIAED subjects). The dosing date and time of the last 3 doses before Titration Period PK visit will be recorded. Note: For PK visits during Maintenance Period (ie, Visits 7 and 8 for non-EIAED subjects, or Visits 8 and 9 for EIAED subjects), as 2 PK samples (1 predose and 1 early postdose [within 1 to 5 hours after dosing]) are to be collected, the following steps are to be followed (revised per Amendment 02):

- Study drug administration in the evening immediately before the PK visits during Maintenance Period will be withheld. All other AEDs should be administered per the subject's usual AED regimen.
- During each of the Maintenance Period PK visits, collect predose PK sample. Then administer study drug on site, followed by early postdose PK sample collection (within 1 to 5 hours after dose administration).
- Bedtime dosing will resume beginning in the evening of the Maintenance Period PK visits.
- The dosing date and time of the study drug dose administered on-site during each Maintenance Period PK visit, as well as the last 2 doses before will be recorded.

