#### 9.5.2 Schedule of Procedures/Assessments

Table 4 and Table 5 present the schedule of procedures/assessments for the Core Study.

Phase			Treatment								
Period	Pretreatment	retreatment Titration Maintenance Follow- Un a								Early Discontinuation	Unscheduled
Visit	1	2 b	3 b	4 c	5°	6 c,d,e	7°	8 c,f	Ср	Discontinuation	
Week	-2	0	2	4	8	12	14	16	20		
Days	-14	1	15	29	57	85	99	113	141		
Procedures/Assessments											
Demography	Х										
Informed consent/assent	Х										
Inclusion/exclusion criteria	Х	Х									
Medical history	Х										
Epilepsy medical history	Х										
Prior and concomitant medication(s)	Х	Х	Х	Х	Х	Х	Х	Х	Х	Х	Х
Prior and concomitant AED(s)	Х	Х	Х	Х	Х	Х	Х	Х	Х	Х	Х
Neurological examination g	Х							Х	Х	Х	
Physical examination h	Х							Х	Х	Х	
Vitals and weight	Х	Х	Х	Х	Х	Х	Х	Х	Х	Х	Х
Height/length h	Х	Х						Х		Х	
Head circumference	Х	Х						Х		Х	
Adverse events	Х	Х	Х	Х	Х	Х	Х	Х	Х	Х	Х
Dispense study drug		Х	Х	Х	Х	Х	Х	Xi			Xj
Retrieve unused study drug			Х	Х	Х	Х	Х	Х		Х	Xj
Study drug compliance			Х	Х	Х	Х	Х	Х		Х	Х
Dispense subject's diary	X k	Х	Х	Х	Х	Х	Х	Х		Х	$X^1$
Retrieve and review subject diary		Х	Х	Х	Х	Х	Х	Х	Х	Х	$X^1$
Clinical laboratory tests m, n	Х					Х		Х	Х	Х	Xº
Thyroid function (TSH, fT3, fT4) and IGF-1 tests	Х							Х		Х	
12-lead ECG p	Х			Х		Х		Х	Х	Х	Xq
Perampanel PK blood sampling r					Х		Х	X		Х	X 
Telephone call s		Х	Х	Х	Х	X	Х	X	Х		
CGI-C, CGI-S t		Х						X		X	
Disposition	Х	Χ						X		Х	

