5.6.5 Electrocardiograms

Descriptive statistics for ECG parameters and changes from baseline will be presented by visit and by age group.

Shift tables will present changes from baseline in ECG interpretation (categorized as normal; abnormal, not clinically significant; and abnormal, clinically significant) to end of treatment.

In addition, the number (percentage) of subjects with at least 1 postbaseline abnormal ECG result in QTcF during the treatment period will be summarized. Clinically borderline and abnormal ECG results in QTcF will be categorized as follows:

Absolute QTc interval prolongation:

- QTc interval 430-450 msec
- QTc interval >450 msec
- QTc interval >500 msec

Change from baseline in QTc interval:

- QTC interval increases from baseline 30-60 msec
- QTC interval increases from baseline >60 msec

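### At ages 2 to <4 years the last Core ECG falls on a withheld-dose visit, and the ECG-before-blood preference steers it ahead of the on-site dose, at reduced exposure mainly in EIAED children

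*Protocol*

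**What the plan says.** **Dosing around PK visits.** Protocol 9.5.1.4 applies a special procedure to ages 2 to <4 years: "For PK visits during Maintenance Period (ie, Visits 7 and 8 for non-EIAED subjects, or Visits 8 and 9 for EIAED subjects"), "Study drug administration in the evening immediately before the PK visits during Maintenance Period will be withheld". A predose sample is drawn, the drug is given on site, and a second sample follows 1 to 5 h later. Bedtime dosing resumes that evening. Infants aged 1 to <24 months keep their evening dose and give one sample per PK visit.

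**ECG schedule.** In Table 4 (non-EIAED) the on-treatment Core ECGs are at Visits 4, 6 and 8. In Table 5 (EIAED) they are at Visits 4, 6, 7 and 9. Only Visit 8 (Table 4) and Visit 9 (Table 5) are also withheld-dose visits. A further ECG is done at Follow-up, four weeks off drug.

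**ECG order.** Protocol 9.5.1.5 says that "ECGs should preferably be recorded prior to blood draws when both are scheduled at the same visit". If the draw comes first, "then the ECG must be recorded at a minimum of 30 minutes after the blood draw". No text places the ECG relative to the on-site dose.

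**Analysis.** SAP 5.6.5 says that "Shift tables will present changes from baseline in ECG interpretation" to end of treatment. ECG parameters and their changes from baseline are summarised by visit and age group. QTcF outliers are counted over any postbaseline ECG in the treatment period. SAP 8.2.2 takes the last non-missing on-treatment value as the Core end-of-treatment value and closes the ECG on-treatment window 14 days after the last dose.

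**The concern.** The withheld-dose procedure and the ECG-order preference each make sense alone. Together they lead a compliant site to record the end-of-Core ECG after a missed dose and before the on-site dose.

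Two summaries are affected. For a child who completes the Core Study, this ECG is normally the end-of-treatment entry in the interpretation shift table, because the Follow-up ECG falls outside the 14-day window. It is also the last by-visit ECG value, shown beside the child's own Visit 6 or 7 reading and, in the age-group tables, beside infants who took the previous evening's dose. A difference in either comparison could reflect the missed dose rather than age or time on drug.

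Because the order is only a preference, some sites may record the ECG before the on-site dose and others after it. Both would be pooled under one visit, and neither document plans to report QTcF with time since dose.

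**Working it through.** The documents give no time since dose for any ECG, so there is no planned figure to reproduce.

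**Inputs**
- Half-life T: about 25 h with an EIAED and 105 h without (Protocol 9.4.1, Other Dosing Considerations).
- Dosing time: before bedtime, no clock time given; assumed 20:00, range 19:00 to 21:00.
- Visit time: the synopsis says that "subjects will attend the clinic any time during the day to provide blood sampling for PK analysis"; assumed 08:00 to 16:00.
- Model: one compartment, instantaneous absorption, steady state at the maintenance dose. The protocol's own model has two compartments, so the results are approximate.

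**1. Time since last dose**
- Ordinary visit: (24 − 20) + 8 = 12 h to (24 − 20) + 16 = 20 h.
- Dose withheld: (48 − 20) + 8 = 36 h to (48 − 20) + 16 = 44 h. With bedtime from 19:00 to 21:00 the range is 35 to 45 h.

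**2. Loss against an ordinary visit at the same dose and clock time**

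Ratio = 2^(−24/T), which does not depend on the assumed clock times.
- EIAED: 2^(−24/25) = 0.514, a fall of 48.6%.
- Non-EIAED: 2^(−24/105) = 0.853, a fall of 14.7%.

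**3. Level as a share of steady-state peak**

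Before the on-site dose the share is 2^(−h/T), with h the hours since the last dose. One dose adds 1 − 2^(−24/T) of peak (0.486 EIAED, 0.147 non-EIAED). At s hours after the on-site dose the share is therefore [2^(−h/T) + 1 − 2^(−24/T)] × 2^(−s/T), with s from 1 to 5.

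| | Ordinary visit, 12–20 h | Withheld, before on-site dose, 36–44 h | 1–5 h after on-site dose |
|---|---|---|---|
| EIAED | 57–72% | 30–37% | 68–83% |
| Non-EIAED | 88–92% | 75–79% | 87–93% |

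EIAED upper end: (0.369 + 0.486) × 2^(−1/25) = 0.83. Lower end: (0.295 + 0.486) × 2^(−5/25) = 0.68.

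**4. Is this the lowest exposure of the study?**

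Superposing the titration steps of Tables 1 and 2 (arbitrary units, 08:00):

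| Maintained dose | Visit 4 | Visit 6 (and 7 if EIAED) | Visit 8/9, dose withheld |
|---|---|---|---|
| Non-EIAED 4 mg | 20.2 | 25.2 | 21.1 |
| Non-EIAED 6 mg | 20.2 | 37.8 | 31.7 |
| EIAED 8 mg | 5.9 | 11.8 | 6.1 |

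The non-EIAED Visit 8 figures omit the on-site dose at Visit 7. At 4 mg it would add 4 × 2^(−336/105) = 0.4, giving 21.5, and 21.5/25.2 = 0.85, in line with step 2.

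Visit 4 is slightly to clearly below the withheld visit in all three cases. Day 8 is far lower (2.1 non-EIAED, 0.7 EIAED), and Follow-up is near zero. One exception concerns on-treatment ECGs only: an EIAED child held at 4 mg would be at about 6.1/2 = 3.0 at Visit 9, below the 5.9 at Visit 4.

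**The case against.** The strongest case against has five parts.

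- **The order is only a preference.** An ECG at least 30 minutes after the predose draw, including one after the on-site dose, already complies. This stands, so the plan does not require a 36 to 44 h reading. The stated default still points there, and nothing directs the alternative.
- **Other ECGs exist.** Visit 6 (non-EIAED) and Visit 7 (EIAED) close Titration, when the dose should have been stable for at least two weeks, and no dose is withheld before them. The Extension adds ECGs at Weeks 28 and 52 (non-EIAED) or 32 and 52 (EIAED), with no PK visits. This stands. A reader might infer that QTcF is assessed only at the low point, but Visits 4, 6 and 7 all count in the outlier summary.
- **The end-of-treatment analysis is narrow.** A reader might infer that QTcF change is also analysed to end of treatment. SAP 5.6.5 specifies only the interpretation shift that way; ECG parameters are summarised by visit.
- **The loss is small without an EIAED.** About 15% is modest. This stands, and the case rests mainly on EIAED children.
- **The consequence is unproven.** Neither document reports a concentration-related QTc effect or plans a concentration-QTc analysis. ECGs are descriptive here, and the cohort may supply as few as one subject to this study. This limits the weight of the point, but comparability within the planned tables is still affected.

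**Conclusion.** The point holds as a comparability weakness that is cheap to remove. At ages 2 to <4 years, the ECG preference and the withheld dose together place the end-of-Core ECG, by default, at an exposure about 49% (EIAED) or 15% (non-EIAED) below an ordinary visit. The effect is material mainly in EIAED children. These percentages rest on the protocol's half-lives, one-compartment decline and steady state. The 36 to 44 h interval rests on assumed clock times.

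What is affected is the Core end-of-treatment entry in the interpretation shift table and the last by-visit ECG summary for this cohort.

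A reader might go further and infer that the ECG is taken at the lowest exposure of the study. The documents do not support that: early titration and Follow-up are lower, and Visit 4 is similar or lower in the modelled cases. It can be called lower than at any ordinary visit on the same maintenance dose.

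**What to change.** **Protocol 9.5.1.5 and footnote p of Tables 4 and 5.** State that, for ages 2 to <4 years at Visit 8 (non-EIAED) or Visit 9 (EIAED), the single 12-lead ECG is recorded after the on-site dose, within the existing 1 to 5 h window, just before the postdose PK draw and at least 30 minutes after any earlier draw. The preference for ECG before blood then applies to the postdose draw.

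**SAP 5.6.5.** List time since last dose with each QTcF value.

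**Cost.** A sentence or two in the protocol and one in the SAP. It is the same ECG at the same visit, recorded while the child is already waiting for the postdose sample, with no change to dosing or sampling.

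**Downside.** The ECG must be timed within the visit and falls closer to a dose than the other ECGs. The modelled level is nevertheless broadly that of an ordinary visit. Without an EIAED it is nearly identical. With an EIAED it is somewhat higher (68–83% of steady-state peak against 57–72%), so it should not be described as near peak. Listing time since dose makes the remaining difference visible.
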